4.3.2 Venetoclax

Chemical Name: 4-{4-[(4'-chloro-5,5-dimethyl[3,4,5,6-tetrahydro[1,1'-biphenyl]]-2-yl)methyl]piperazin-1-yl}-N-(3-nitro-4-{[(oxan-4-yl)methyl]amino}benzene-1-sulfonyl)-2-[(1H-pyrrolo[2,3-b]pyridine-5-yl)oxy]benzamide.

Formulation, preparation, storage and stability: Please see venetoclax USPI⁵².

Route of Administration: Venetoclax should be taken PO, with food, at a dose of 400 mg daily once the ramp-up phase is completed. During the 5-week ramp-up in Cycle 1, venetoclax is given PO at the dose of 20 mg during Week 1, 50 mg during Week 2, 100 mg during Week 3, 200 mg during Week 4, and 400 mg during Week 5. Use of posaconazole and strong CYP inhibitors is contraindicated in the ramp up phase. For patients receiving a steady daily dose of venetoclax, the dose of venetoclax should be modified accordingly to account for changes in concomitant use of posaconazole and CYP inhibitors in accordance with the venetoclax USPI⁵².

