5.1.2 Venetoclax

In Cycle 1, treatment with venetoclax should be administered over a 5-week ramp up period per the USPI (refer to [Table 4](#) below). The 5-week ramp-up dosing schedule is designed to gradually reduce tumor burden (debulk) and decrease the risk of TLS⁵³. After the ramp-up phase is completed, venetoclax at a dose of 400 mg should be taken PO once daily with a meal and water, at approximately the same time every day. Note that on Day 1 of Cycle 1, venetoclax will be taken 1 hour prior to administration of the APR-246 infusion.

Table 4. Dosing Schedule for Ramp-Up Period in Cycle 1

Week Number	Venetoclax Daily Dose
Week 1	20 mg
Week 2	50 mg
Week 3	100 mg
Week 4	200 mg
Week 5 and beyond	400 mg

If required, any dosage modifications of venetoclax are presented in Section [5.3.3](#).

Detailed instructions on administration of venetoclax can be found in the Pharmacy Binder and current USPI⁴⁷.

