5.3.3.2 Management of Potential Venetoclax Interactions with CYP3A and P-gp Inhibitors

Table 15. Venetoclax Dose Modifications for Use with CYP3A Inhibitors

Co-administered Drug	Initiation and Ramp-Up Phase	Steady Daily Dose (After Ramp-Up Phase) ^a
Posaconazole	Contraindicated	Reduce venetoclax dose to 70 mg
Other strong CYP3A inhibitor	Contraindicated	Reduce venetoclax dose to 100 mg
Moderate CYP3A inhibitor	Reduce venetoclax dose by at least 50%	
P-gp inhibitor		

^a Consider alternative medications or reduce the venetoclax dose as described in table.

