5.3.3.3 Tumor Lysis Syndrome

TLS, including fatal events and renal failure requiring dialysis, has occurred in patients with high tumor burden when treated with venetoclax.

Venetoclax can cause rapid reduction in tumor and thus poses a risk for TLS at initiation and during the ramp-up phase. Changes in blood chemistries consistent with TLS that require prompt management can occur as early as 6 to 8 hours following the first dose of venetoclax and at each dose increase.

The risk of TLS is a continuum based on multiple factors, including tumor burden and comorbidities. Reduced renal function further increases the risk. Patients should be assessed for risk and should receive appropriate prophylaxis for TLS, including hydration and antihyperuricemics. Monitor blood chemistries and manage abnormalities promptly. Interrupt dosing if needed. Employ more intensive measures (IV hydration, frequent monitoring, hospitalization) as overall risk increases.

Concomitant use of venetoclax with P-gp inhibitors or strong or moderate CYP3A inhibitors increases venetoclax exposure, may increase the risk of TLS at initiation and during ramp-up phase and requires venetoclax dose adjustment.

Table 16. Recommended TLS Prophylaxis Based on Tumor Burden in Patients

Tumor Burden	Prophylaxis		Blood Chemistry Monitoring ^{c,d}
	Hydration ^a	Anti-hyperuricemics	

		Assessments		
Low	All LN <5 cm AND ALC $<25 \times 10^9/L$	Oral (1.5-2 L)	Allopurinol ^b	Outpatient 
 For first dose of 20 mg and 50 mg: Pre-dose, 6 to 8 hours, 24 hours For subsequent ramp-up doses: Pre-dose
Medium	Any LN 5 cm to <10 cm OR ALC $\geq 25 \times 10^9/L$	Oral (1.5-2 L) and consider additional IV	Allopurinol	Outpatient: 
 For first dose of 20 mg and 50 mg: Predose, 6 to 8 hours, 24 hours For subsequent ramp-up doses: Predose For first dose of 20 mg and 50 mg: Consider hospitalization for patients with creatinine CL <80 mL/min; see below for monitoring in hospital
High	Any LN ≥ 10 cm OR ALC $\geq 25 \times 10^9/L$ AND any LN ≥ 5 cm	Oral (1.5-2L) and IV (150-200 mL/h as tolerated)	Allopurinol; consider rasburicase if baseline uric acid is elevated	In hospital 
 For first dose of 20 mg and 50 mg: Pre-dose, 4, 8, 12 and 24 hours Outpatient 
 For subsequent ramp-up doses: Pre-dose, 6 to 8 hours, 24 hours

ALC = absolute lymphocyte count; LN = lymph node.

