APPENDIX VI - Dose Modifications of Venetoclax with Use of CYP3A or P-gp Inhibitors

Concomitant use of venetoclax with *strong* CYP3A inhibitors at initiation and during ramp-up phase is contraindicated. Concomitant use of venetoclax with *strong* CYP3A inhibitors increases venetoclax exposure (i.e., C_{max} and AUC) and may increase the risk for TLS at initiation and during ramp-up phase. For patients who have completed the ramp-up phase and are on a steady daily dose of venetoclax, reduce the venetoclax dose by at least 75% when *strong* CYP3A inhibitors must be used concomitantly.

Avoid concomitant use of venetoclax with *moderate* CYP3A inhibitors or P-gp inhibitors. Consider alternative treatments. If a *moderate* CYP3A inhibitor or a P-gp inhibitor must be used, reduce the venetoclax dose by at least 50%. Monitor these patients more closely for signs of toxicities.

Resume the venetoclax dose that was used prior to initiating the CYP3A inhibitor or P-gp inhibitor 2 to 3 days after discontinuation of the inhibitor.

The recommendations for managing drug-drug interactions are summarized in the table below.

Co-administered drug	Initiation and Ramp-Up Phase	Steady Daily Dose (After Ramp-Up Phase)
Posaconazole	Day 1 – 10 mg Day 2 – 20 mg Day 3 – 50 mg Day 4 – 70 mg	Reduce venetoclax dose to 70 mg.
Other strong CYP3A inhibitor	Day 1 – 10 mg Day 2 – 20 mg Day 3 – 50 mg Day 4 – 100 mg	Reduce venetoclax dose to 100 mg.
Moderate CYP3A inhibitor	Reduce the venetoclax dose by at least 50%	
P-gp inhibitor		

Warfarin

Concomitant use of venetoclax increases warfarin C_{max} and AUC_{inf} , which may increase the risk of bleeding. Closely monitor international normalized ratio (INR) in patients using warfarin concomitantly with venetoclax.

P-gp Substrates

Concomitant use of venetoclax increases C_{max} and AUC_{inf} of P-gp substrates, which may increase toxicities of these substrates. Avoid concomitant use of venetoclax with a P-gp substrate. If a concomitant use is unavoidable, separate dosing of the P-gp substrate at least 6 hours before venetoclax.

Please refer to the venetoclax USPI⁵⁶ for additional details on drug-drug interactions.

Below (Table 20) are examples of CYP3A inhibitors and inducers (strong and moderate); however,

this is not an exhaustive list.

Table 20. CYP3A Inhibitors and Inducers

CYP3A Inhibitors	
Strong CYP3A Inhibitors	Moderate CYP3A Inhibitors

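### Appendix VI gives four-day venetoclax ramp-up doses with posaconazole and other strong CYP3A inhibitors, combinations that the protocol contraindicates during ramp-up

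*Combined protocol and SAP*

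**What the plan says.** Three places forbid the combination:

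- Appendix VI, opening sentence, on strong inhibitors: "CYP3A inhibitors at initiation and during ramp-up phase is contraindicated".
- Section 4.3.2: "Use of posaconazole and strong CYP inhibitors is contraindicated in the ramp up phase".
- Section 5.3.3.2, Table 15, ramp-up column: "Other strong CYP3A inhibitor Contraindicated". The posaconazole row has the same entry.

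One place doses it. The Appendix VI table is introduced with "The recommendations for managing drug-drug interactions are summarized in the table below". Its initiation and ramp-up column then gives, for other strong CYP3A inhibitors, "Day 1 – 10 mg Day 2 – 20 mg Day 3 – 50 mg Day 4 – 100 mg". For posaconazole it gives 10, 20, 50 and 70 mg on Days 1 to 4. Table 20 lists posaconazole among the strong inhibitors, so the opening sentence of the appendix covers both rows.

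The trial's own ramp-up (Section 5.1.2, Table 4) is 20, 50, 100, 200 and 400 mg daily in Weeks 1 to 5. No four-day schedule appears anywhere else.

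**The concern.** A site that takes the table at its word would give a contraindicated combination and raise the dose every day. The protocol's reason for the slow ramp-up is tumor lysis syndrome (TLS): "The 5-week ramp-up dosing schedule is designed to gradually reduce tumor burden (debulk) and decrease the risk of TLS". Section 5.3.3.3 says that the blood chemistry changes "can occur as early as 6 to 8 hours following the first dose of venetoclax and at each dose increase", and that "TLS, including fatal events and renal failure requiring dialysis, has occurred in patients with high tumor burden when treated with venetoclax".

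The situation is foreseeable. Exclusion criterion 19 covers only current treatment with certain strong inhibitors at entry. After entry, Table 8 asks sites to consider antifungal prophylaxis during neutropenia, and Section 5.3.2.3 expects that triazole antifungals may be started on study. Table 20 lists posaconazole, voriconazole and itraconazole as strong.

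Trial conduct is exposed as well. Cycle 1 lies in the DLT window (Section 5.1.4). A resulting toxicity could count as a DLT unless an exemption applies. The relevant exemption is a first grade 3 electrolyte abnormality and/or fall in creatinine clearance that improves to grade 2 (or to a baseline of grade 2 or higher) within 48 hours on supportive treatment. With three to six patients per cohort, one DLT among the first three triggers expansion and two stop escalation. Under Section 8.4, a death that cannot be put down entirely to the disease suspends enrollment.

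**Working it through.** **1. Is this an extraction fault?** The steady-dose column of the same table can be checked. It gives 100 mg and 70 mg, as Table 15 does. Against 400 mg these are reductions of 1 − 100/400 = 75% and 1 − 70/400 = 82.5%, both consistent with the appendix's minimum of 75%. The rows for moderate CYP3A and P-gp inhibitors also agree with Table 15. Only the two strong-inhibitor ramp-up cells conflict.

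**2. Worst case: inhibitor on board when venetoclax starts.** Nominal daily doses in mg, from Table 4 and Appendix VI:

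| | Day 1 | Day 2 | Day 3 | Day 4 | Total |
|---|---|---|---|---|---|
| Trial ramp-up, Week 1 | 20 | 20 | 20 | 20 | 80 |
| Other strong inhibitor | 10 | 20 | 50 | 100 | 180 |
| Posaconazole | 10 | 20 | 50 | 70 | 150 |

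- Day 4 ratio: 100/20 = 5; posaconazole 70/20 = 3.5.
- Days 1 to 4 total: 180/80 = 2.25; posaconazole 150/80 = 1.875.
- Increases within Days 1 to 4: three in each table row. The trial's first increase is at Week 2, which is Day 8, so it has none.
- Timing: 50 mg comes on Day 3 instead of Day 8, 5 days early, in both rows. In the other-strong-inhibitor row, 100 mg comes on Day 4 instead of Day 15, 11 days early. The posaconazole row stops at 70 mg.
- The table's Day 1 dose is lower than the trial's (10 against 20 mg).

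**3. Inhibitor started later in Cycle 1.** Read literally, Days 1 to 4 have passed and the cells no longer apply. Read as a restart at 10 mg:

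- Week 2 (scheduled 50 mg): only the fourth day is higher, 100/50 = 2 times, or 70/50 = 1.4 times with posaconazole. The four-day total is lower: 180 or 150 mg against 4 × 50 = 200 mg. The table does not say what follows Day 4. If that dose were held, the excess would end at the latest when the schedule reaches 100 mg on Day 15.
- Weeks 3 to 5 (scheduled 100, 200, 400 mg): the table's maximum of 100 mg never exceeds the schedule.

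**4. Which source governs?** Section 5.1.2 directs sites to Section 5.3.3 for venetoclax dose modifications, and Table 15 there is correct. Exclusion criterion 19 directs them to Appendix VI, where the table is offered as the summary. No visible text ranks the two. Appendix VII, the handout on prohibited medications, is not in the text available for review, so this statement covers visible text only.

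**The case against.** The strongest reply is that the right rule is easy to find. It stands in three places, one of them a few lines above the faulty table, and Section 5.1.2 points to the correct one. Exclusion criterion 19 removes some users of strong inhibitors at entry. The patient diary repeats the five-week schedule, and Table 16, footnote d, asks for chemistry checks at each subsequent ramp-up dose in patients at risk. All of this stands. It lowers the chance that a site follows the wrong cells, and that chance is unknown. It does not make the cells right.

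A second reply is that the first four days are a selective window. If the Day 4 dose were simply continued through the 35 days of Cycle 1, the table would give 180 + 31 × 100 = 3,280 mg (posaconazole 150 + 31 × 70 = 2,320 mg) against 7 × (20 + 50 + 100 + 200 + 400) = 5,390 mg. That is 39% (57%) less nominal drug. The arithmetic is correct, but nominal dose is not exposure. By the protocol's own account TLS follows the first dose and each increase, so the early days are the relevant ones. The reply does require that the figures in step 2 be labelled a worst case.

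A reader might also infer that Section 5.3.3.3 permits the combination, because it groups strong, moderate and P-gp inhibitors in one sentence asking for dose adjustment. It does not. That sentence follows directly on Table 15 and does not lift the contraindication.

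**Conclusion.** The two strong-inhibitor ramp-up cells in Appendix VI are wrong as written, and the point stands as a two-cell safety correction. In the worst case the nominal Day 4 dose is 5 times the scheduled dose (3.5 times with posaconazole), with three increases in four days. This assumes that the inhibitor is on board when venetoclax starts and that the site follows the table. For a later start in Cycle 1 the nominal excess is small or absent.

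Two stronger readings are tempting and unsupported. One treats the steady-dose reductions as exposure ratios (400/100 = 4 and 400/70, about 5.7) and concludes that the table reaches the equivalent of 400 mg on Day 4. The documents give those reductions as dosing rules and state no exposure ratio. The other concludes that the error will distort DLT counts or the MTD. That depends on how often sites would follow the cells and on what toxicity would result, and the documents give neither figure.

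**What to change.** In the Appendix VI table, replace both strong-inhibitor entries in the initiation and ramp-up column (posaconazole, and other strong CYP3A inhibitor) with Contraindicated, matching Table 15 and Section 4.3.2. Optionally, repeat the contraindication in Section 5.3.3.3 and say that dose adjustment during ramp-up applies to moderate CYP3A and P-gp inhibitors. The cost is two table cells and, if wanted, one sentence.

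A separate minor correction, unrelated to this point, can go into the same amendment. Section 6.6.2 lists rituximab at 500 mg/m² for Day 2 of all of Cycles 2 to 7. It should read 375 mg/m² in Cycle 2 and 500 mg/m² in Cycles 3 to 7, as in Section 5.1.3.
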